9.7 Analysis of pharmacokinetic parameters

Analysis of pharmacokinetic parameters in the respective group (n = 20) shall be performed by the variable of quantitative change of serum immunoglobulin IgG concentrations in patients (in grams per litre of blood) at protocol-specified time points.

For the aforementioned quantitative variable, provide descriptive statistics (n, arithmetic mean, standard deviation, the median and the percentiles, the minimum and maximum values—depending on the type of distribution) for each visit according to patient assessment schedule, and for the (Ti – T-baseline) differences.

Determine the relative change in the quantitative variable based on its mean values from the following formula:

$$X(\%) = (Ti - T_{\text{baseline}})/T_{\text{baseline}} * 100,$$

where T-baseline is the arithmetic mean of the variable at baseline (screening visit) and Ti is the arithmetic mean of the analysed variable at subsequent visits.

Plot graphs of changes of mean values over time (for normally distributed data) or changes of median values over time (for non-normally distributed data) for the variable.

Assess the significances of changes in these values in each group using Student's t-test for paired data or a Wilcoxon signed rank test depending on the normality of distribution of individual (Ti – T-baseline) differences, the latter tested using the Shapiro–Wilk's test.

For the variables measured according to the schedule of patient assessments more often than twice, evaluate the changes in quantitative variables over time using a one-way analysis of variance (ANOVA) or rank analysis depending on the normality of the distribution, checked using the Shapiro–Wilk test. In this setting, the dependent variable is the parameter being analysed, and the “visit” factor is the fixed parameter. Evaluate the value and significance for the reliability of the difference between the visits using post hoc analysis with Tukey's test (for ANOVA) or the Wilcoxon signed rank test with Holm's adjustment (for the rank test). To verify the preconditions for the use of analysis of variance, the normal distribution of residuals will be tested using the Shapiro–Wilk test. If the residuals are not distributed normally, a corresponding rank analysis will be performed. Assessment of pharmacokinetic parameters will be informed by fundamental principles of descriptive statistics for the main pharmacokinetic parameters, preliminary assessment of statistical homogeneity of study patient population, as well as by the obtained values for the parameters and the homogeneity of their distribution.

For each patient, individual pharmacokinetic parameters will be calculated:

Cmax, the maximum serum concentration of the analyte;

AUC0-t, the area under the concentration-time PK curve (from zero to last blood sampling, where the concentration of the analyte is higher than or equal to the lower limit of quantification [LLOQ]);

AUC0-∞, the area under the concentration-time PK curve (from zero to infinity).

Tmax, the time to maximum concentration of the analyte;

t1/2, the elimination half-life of the analyte;

Kel, the elimination rate constant of the analyte;

IR, the incremental recovery of class G immunoglobulin;

Vd, volume of distribution;

Cl, serum clearance;

$((AUC_{0-\infty} - AUC_{0-t})/AUC_{0-\infty})$, the residual (extrapolated) area (AUCextrapol).

The values of Cmax and Tmax were calculated using a model-independent method, as the largest of the measured concentrations in each patient and as a corresponding time of observed maximum, respectively.

AUC0-t was calculated using trapezoidal method.

All other parameters were calculated using a model-independent method.

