4.2. Description of the design

Study design: Open-label, multicentre, single-arm, cohort, uncontrolled, prospective clinical study of tolerability, safety and pharmacokinetics of the medicinal product BP-SCIG 20% for subcutaneous administration with further assessment of efficacy in long-term use.

[figure not shown]

Fig. 1 Study diagram

Number of patients:

56 patients with PID – adults, adolescents, and children.

Patients older than 18 years – at least 20 patients

Patients younger than 18 years – at least 20 patients across different age groups:

- 0 to \leq 2 years – at least 2;
- $>$ 2 to \leq 6 years – at least 4;
- $>$ 6 to \leq 12 years – at least 7;
- $>$ 12 to \leq 18 years – at least 7.

The first 10 patients enrolled in the study must be adults, for an interim safety assessment in adult patients who received at least 4 infusions of the IMP BP-SCIG 20%.

Based on the results of such assessment, the possibility of enrolling patients younger than 18 years of age is determined. The interim report will be reviewed and assessed by the Independent Safety Committee.

In the pharmacokinetic assessment:

- the threshold IgG levels are determined in at least 40 patients, at least 20 of whom must be children and adolescents before the age of 18 years.
- pharmacokinetic parameters (AUC, Cmax, Tmax, $T_{1/2}$, K_{el} , Cl, IR, Vd) are determined in no less than 20 adult patients
- confirmation of the dose adjustment factor (adult patients of cohort B)

Groups:

This study does not involve the distribution of patients into groups. Of patients in all age categories who meet inclusion criteria and passed the screening, and who do not meet any of the non-inclusion (exclusion) criteria, one group is formed, which will receive the investigational product.

The following cohorts are formed from the general group to assess pharmacokinetics:

Cohort A: the patients who have already received subcutaneous immunoglobulin (SCIG);

Cohort B: the patients who previously received intravenous IgG IVIG; **Cohort C:** newly identified patients who have not received treatment with IgG product yet.

Also, PK assessment subgroups are formed from the general group of patients to determine threshold IgG levels (in at least 40 patients, at least 20 of whom must be children and adolescents younger than 18 years), to determine pharmacokinetic parameters (at least 20 adults), and to confirm the dose adjustment factor (adult patients previously receiving BIOVEN).

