Since patients were distributed across cohorts, the required number of patients in each cohort was established in accordance with the recommendations of the U.S. Department of Health and Human Services Food and Drug Administration (FDA) regarding the safety, pharmacokinetics and effectiveness studies of immunoglobulin in primary immunodeficient conditions. According to that guidance document, the optimal number of patients in subgroups for pharmacokinetic assessment (adult patients) ranges from 6 to 12, to obtain a reliable assessment of variability. Considering these recommendations, the number of patients in the cohorts for adult patients was determined to be between 8 and 10.

During the Data Analysis phase, it is envisaged to allow assessment of patients based on the identified covariates.

Study phases.

The patient/their legally authorised representative/the patient's parents should sign informed consent.

After signing the informed consent, the screening examinations are performed, and patient's eligibility is assessed against inclusion/non-inclusion criteria.

During the screening phase, verification of PID diagnosis is required (according to the ESID criteria) based on source documentation data (see Section 6.3.3 of the Protocol).

- **Screening period:**

- Visit 1: Day 0 – signing the ICF, determination of IgG levels*
- Visit 2: Day 21–28 (range: 21–28 days) – determination of IgG levels*
- Visit 3: Day 42–56 (range: 21–28 days) – determination of IgG levels*. Determination of pharmacokinetic parameters of BIOVEN in patients aged over 18 years who have previously received therapy with BIOVEN (7 blood sampling points additionally)

*For the group of patients from Cohorts A and B who have already received SCIG or IVIG, an assessment of monthly threshold IgG levels is performed during prior treatment (the prior treatment continues).

The screening period is different across different cohorts:

- For Cohort A, patients who have previously received SCIG are required to undergo Visits 1 and 2 of the screening period. In the event of meeting the criterion “total serum IgG level ≥ 5 g/L – as confirmed by the results of at least two (2) measurements performed immediately prior to the subsequent administration of SCIG after signing the ICF”, the patient proceeds to treatment with the IMP BP-SCIG 20%, starting from Cycle 1. If the criterion is not met, then Visit 3 is performed.
- For Cohort B, patients who have previously received IVIG:

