The assessment of threshold (trough) IgG levels is to be performed in at least 40 patients enrolled in the CT; of these, 20 subjects must be children or adolescents with an appropriate age distribution for this patient group. The trough levels of the IgG from the investigational medicinal product must be assessed after 4 months of treatment with the IMP, prior to the next infusion, once every 4 weeks (once per month/treatment cycle) over 6 months.

The obtained monthly trough IgG levels shall be compared with the trough levels for at least two prior infusions of the previous SCIG or IVIG product. Alternatively, for treatment-naïve patients, a descriptive comparison with published literature (if available) is performed.

Phase of IVIG pharmacokinetic assessment

This phase includes patients older than 18 years who had been receiving previous therapy with the medicinal product BIOVEN prior to their study entry and, accordingly, throughout the screening period.

PK will be assessed through an additional sampling of 3.5 mL of venous blood (per one sampling, a total of 8–9 sampling time points) for subsequent determination of patient's levels of plasma immunoglobulin in the samples over 21–28 days after the infusion of BIOVEN. The total volume of venous blood for the entire IVIG PK assessment per one patient is 28–31.5 mL.

The data obtained during the phase of BIOVEN pharmacokinetics will be used to confirm or recalculate the dose adjustment factor for switching from IVIG to the IMP.

The assessment begins at Visit 3 of the screening period (see Table 4.2.3 Pharmacokinetic assessment of IVIG – BIOVEN). The time of blood sampling is documented.

Phase of IMP BP-SCIG 20% pharmacokinetic assessment

This phase includes at least 20 patients older than 18 years who had been receiving the investigational medicinal product for at least 4 months, and did not have any severe bacterial complications during the trial.

PK will be assessed through an additional sampling of 3.5 mL of venous blood (per one sampling, a total of 8 sampling time points) for subsequent determination of patient's levels of plasma immunoglobulin in the samples over 7 days after the infusion of the IMP BP-SCIG 20%. The total volume of venous blood for PK assessment for one patient is 28 mL.

The assessment is performed at Week 21 (see Table 4.2.2 – Pharmacokinetic assessment of the IMP). The time of blood sampling is documented.

Study phases. Follow-up and completion of the study

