5.1. Inclusion Criteria

Table 5.1.1 – Inclusion criteria for CT subjects

No.	Inclusion criterion
1.	a signed informed written consent of the patient/patient's parents or legally authorised representative to take part in the study;
2.	children from 0 to 18 years of age, of both sexes; or adult patients: males and females older than 18 years;
3.	a diagnosis of primary immunodeficiency with impaired antibody production document-supported according to the ESID criteria, requiring replacement therapy with immunoglobulins;
4.	patients with a body weight of no less than 9.1 kg;
5.	patients who received replacement therapy with intravenous immunoglobulin (IVIG) products at intervals from 21 to 28 days at the dose of 0.4–0.8 g/kg, for at least 4 months prior to the start of the study and have total serum IgG levels ≥ 5 g/L*, which is confirmed by the results of no less than 2 measurements performed immediately before the scheduled IVIG administration after signing the ICF, or patients who received replacement therapy with subcutaneous immunoglobulin (SCIG) products at the dose of 0.4–0.8 g/kg per month, for at least 4 months prior to the start of the study, and have total serum IgG levels ≥ 5 g/L*, based on the results of no less than 2 measurements performed immediately before the scheduled SCIG administration after signing the ICF; or patients with a newly established diagnosis of PID who have not yet received replacement therapy with IgG products (treatment-naïve patients) and have a serum IgG level ≤ 4 g/L;
6.	absence of episodes of serious bacterial infections (bacteraemia or sepsis, bacterial meningitis, osteomyelitis/septic arthritis, bacterial pneumonia, visceral abscess) while taking the previous medicinal product and absence of episodes of hospitalisation for at least 3 months prior to inclusion in the study and during the screening period (prior to the first administration of the IMP BP-SCIG 20%);
7.	a negative pregnancy test (in female patients with childbearing potential); readiness to use reliable methods of contraception throughout the study period;
8.	patient's ability, in the Investigator's judgement, to comply with all the requirements of the study protocol.

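### Section 9.7 measures IgG change from screening in one adult group without separating treatment-naive from switched patients, so a fall after switching can be diluted or hidden

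*Protocol*

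**What the plan says.** Section 9.7 names one analysis set: "Analysis of pharmacokinetic parameters in the respective group (n = 20) shall be performed by the variable of quantitative change of serum immunoglobulin IgG concentrations". The relative change X(%) is built from two group means. Its reference term is defined by the words "where T-baseline is the arithmetic mean of the variable at baseline (screening visit"); the other term is the corresponding group mean at a later visit. The significance of change is then assessed with a paired t-test or a Wilcoxon signed rank test, "depending on the normality of distribution of individual (Ti – T-baseline) differences". Where there are more than two visits, an ANOVA or rank analysis with visit as the factor is added. None of these is split by previous therapy.

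Entry to the group is set in section 4.2: "This phase includes at least 20 patients older than 18 years who had been receiving the investigational medicinal product for at least 4 months", and without severe bacterial complications. Section 6.3.9 repeats this. Table 5.3.2 removes only patients with less than 4 months of product or with a serious bacterial infection at the time of the PK assessment. Previous therapy is not a condition.

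Section 5.1, criterion 5, admits three kinds of patient: those on IVIG and those on SCIG, both with pre-dose IgG of at least 5 g/L, and patients "who have not yet received replacement therapy with IgG products", with IgG of at most 4 g/L. Section 4.2 calls these Cohorts B, A and C. It also says that, for treatment, "one group is formed, which will receive the investigational product", and that "the number of patients in the cohorts for adult patients was determined to be between 8 and 10".

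**The concern.** Baseline does not mean the same thing throughout the group. In Cohorts A and B it is IgG on the previous product, so the change shows what the switch did. In Cohort C it is untreated IgG, so the change shows what starting replacement did. Section 6.1 aims for a trough of at least 5–6 g/L, so naive patients are expected to rise. One mean and one p-value over both kinds of patient answer neither question, and the mixture leans in the product's favour. A reader could take a flat or positive X(%) as evidence that IgG was maintained after switching when it had fallen.

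**Working it through.** **Inputs from the protocol.** n = 20 (9.7); naive screening IgG at most 4 g/L and switched at least 5 g/L (5.1); significance level 0.05 for these tests (9.8). The protocol gives no derivation or expected change for n = 20, so there is no stated figure to reproduce.

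**Are naive adults in the group?** Nothing excludes them. Section 3 asks for PK parameters to be compared between cohorts, and sections 4.2 and 6.3.9 determine the product's parameters in adults only, so naive adults must be among the 20 if Cohort C is to be part of that comparison. Their number is not fixed. If the three adult cohorts were equal in size, it would be 20/3, or 6 to 7.

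**Assumptions, not in the protocol.** Switched mean B = 8 g/L, naive mean N0 = 3 g/L, the same proportional fall d in every switched patient, and one on-treatment level P = B(1 - d) for everyone.

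**Formula**, with k naive of 20:

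- Pooled baseline = [k·N0 + (20 - k)·B] / 20
- Pooled on-treatment mean = [k·P + (20 - k)·B(1 - d)] / 20, which equals P here
- X = on-treatment mean / baseline - 1

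With k = 2 the baseline is (6 + 144)/20 = 7.5; with k = 6 it is (18 + 112)/20 = 6.5. For d = 10%, P = 7.2: 7.2/7.5 - 1 = -4.0% and 7.2/6.5 - 1 = +10.8%. For d = 20%, P = 6.4: 6.4/7.5 - 1 = -14.7% and 6.4/6.5 - 1 = -1.5%.

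| Naive of 20 | Pooled baseline, g/L | X, true 10% fall | X, true 20% fall |
|---|---|---|---|
| 0 | 8.0 | -10.0% | -20.0% |
| 2 | 7.5 | -4.0% | -14.7% |
| 4 | 7.0 | +2.9% | -8.6% |
| 6 | 6.5 | +10.8% | -1.5% |
| 7 | 6.25 | +15.2% | +2.4% |

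**Break-even** (X = 0): k = 20·dB / (dB + P - N0). For 10%, 20 × 0.8/(0.8 + 4.2) = 3.2 patients. For 20%, 20 × 1.6/(1.6 + 3.4) = 6.4 patients.

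**Wider range.** Take B from 6 to 10, N0 from 2 to 4, and P either the switched level or 6 g/L. With 6 to 7 naive of 20, a 10% fall reads anywhere from -1% to +25% and a 20% fall from -11% to +14%. Break-even runs from 2.5 to 6.7 naive patients for a 10% fall and from 4.6 to 12 for a 20% fall.

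**The paired test.** With k = 6 and d = 10%, naive patients change by 7.2 - 3 = +4.2 g/L and switched patients by 7.2 - 8 = -0.8 g/L. The mean difference is (6 × 4.2 - 14 × 0.8)/20 = +0.7 g/L. The mixture alone gives an SD of 5 × √(0.3 × 0.7) ≈ 2.3 g/L, so the sign turns and the noise grows.

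The 9.7 rule (Shapiro–Wilk at 0.01, then paired t or Wilcoxon at 0.05) was simulated 2,000 times per setting, with B = 8, between-patient SD 1.5, within-patient CV 10% and N0 = 3. The chance of a significant decrease was:

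| Naive of 20 | 10% fall | 20% fall |
|---|---|---|
| 0 | 99% | 100% |
| 2 | 54% | 100% |
| 4 | 0% | 6% |
| 6 or more | 0% | 0% |

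A paired t-test in the switched patients alone found the 10% fall in 98% of runs (2 naive, 18 switched) down to 89% (8 naive, 12 switched), and the 20% fall in about 100%.

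**The case against.** The strongest reply is that section 9.7 is not where the protocol asks whether IgG holds after switching. Section 9.6 names AUC and trough IgG as the main PK parameters. It compares AUC with BIOVEN for the relevant cohorts and troughs with at least two infusions of the previous product, and limits naive patients to a descriptive comparison with the literature. This stands. No success criterion rests on X(%), and the formal conclusion in section 9.10 concerns serious bacterial infections. A reader might infer that the primary PK comparison is masked; if section 9.6 is followed, it is not.

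It can also be said that pooling is only inferred. Section 4.2 forms Cohorts A to C for pharmacokinetics and allows for covariates, section 9.7 speaks of testing within each group and of checking homogeneity, and section 9.6 mentions ANCOVA for baseline differences. But section 4.2 states that patients are not distributed into groups, the within-group phrase belongs to the test and not to X(%), and none of the other remarks names prior therapy or removes Cohort C. The formula, baseline and group are fixed in the protocol, so this is not a detail merely left to the SAP.

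Finally, section 9.7 also asks for medians, percentiles, minimum and maximum of the differences. Falls in individuals would be visible there, though not in X(%) or its p-value.

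**Conclusion.** The point holds for the section 9.7 change-from-screening analysis and its tests. As written, they mix the effect of starting replacement with the effect of switching product, in a direction that favours the product. It is a flaw in a supporting analysis and does not undermine the main PK comparison.

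The size depends on figures that the protocol does not give: the number of naive adults among the 20, the mean IgG by cohort, and the level reached on treatment. With 2 naive patients a fall is diluted. Under the 8 and 3 g/L assumption, a 10% fall is fully hidden from 4 naive patients upward, and a 20% fall from 7.

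Two stronger readings are tempting. One is that a 10–20% fall in every switched patient would be hidden because a third of the group is planned to be naive. The document gives 8 to 10 adults in the cohorts but sets no naive share for the 20, and under other plausible values a 20% fall would still read as a fall. The other is that section 9.4 has the same fault. Its IgG variable is dichotomous (at least 5 g/L or not), so the mean-change formula does not apply to it.

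**What to change.** In section 9.7, compute X(%), the paired test and the visit analysis separately by cohort, or in Cohorts A and B only, and label the result as change from previous therapy. Report Cohort C on its own, descriptively, as the rise from untreated IgG. This brings section 9.7 into line with section 9.6. State in the same place how many patients of each cohort enter the PK group. Averaging within-patient ratios instead of taking a ratio of group means is optional and does not by itself cure the pooling. The change is one of wording and needs no new data or visits. The cost is fewer patients per table and wider intervals within each cohort.

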9.8 Levels of significance

The significance level for the Shapiro–Wilk test and for the primary efficacy variable shall be set at 0.01; for other statistical tests, it shall be set at 0.05.

9.9 Working with missing or incomplete data

Missing or incomplete data shall be replaced using the Last-Observation-Carried-Forward (LOCF) method. Or by rank aggregation technique for rows where the last observation carried forward is not applicable.

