PK will be assessed through an additional sampling of 3.5 mL of venous blood (for one sampling) for subsequent determination of patient's levels of immunoglobulin in the samples over 21–28 days after the infusion of BIOVEN. The total volume of venous blood for the PK assessment per one patient is 28–31.5 mL.

The procedures are performed at Visit 3 of the screening period (Table 4.2.3. Pharmacokinetic assessment of IVIG). The time of blood sampling is documented.

Structure of PK assessment of IVIG

- 1 PK0 (pre-administration) Before administration of BIOVEN (10–30 min prior)
- 2 PK1 (15 min) 15 minutes after administration of BIOVEN (± 10 min)
- 3 PK2 (1 hour) 1 hour after administration of BIOVEN (± 15 min)
- 4 PK3 (1 day) 24 hours after administration of BIOVEN (± 5 h)
- 5 PK4 (3 days) 72 hours after administration of BIOVEN (± 5 h)
- 6 PK5 (7 days) 7 days after administration of BIOVEN (± 5 h)
- 7 PK6 (14 days) 14 days after administration of BIOVEN (± 5 h)
- 8 PK7 (21 days) 21 days after administration of BIOVEN (± 5 h)
- 9 PK8 (28 days) 28 days after administration of BIOVEN (± 5 h) (where applicable)

The points for pharmacokinetic assessment of BIOVEN were selected based on previous PK studies of BIOVEN.

The data obtained during the phase of BIOVEN pharmacokinetics will be used to confirm or recalculate the dose adjustment factor for switching from BIOVEN to the IMP.

The procedures of preparation for analysis, collection, storage, transportation of biological material, and completion of accompanying documentation are carried out in accordance with the regulations described in the Laboratory Manual.

Blood collection can be performed, at the study doctor's discretion, in a hospital, on an outpatient basis or by a Sponsor-designated Central Laboratory, in a collection point (if the study subject is mobile in the Investigator's judgement), or by a mobile team.

In the event of deterioration of the patient's well-being or the patient's desire to withdraw from the study, blood sample collection is discontinued. Information about these cases shall be entered in the eCRF, source documentation, and reported to the Sponsor.

In the event a sample was not collected according to the protocol-scheduled time (missed), the information explaining that event shall be entered in the eCRF and source documentation, and sample collection shall be resumed at the next time scheduled according to the Schedule.

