6.3.16 Analysis of deviations from bioanalytical testing plan

All deviations from the initial statistical analysis plan will be described and justified in the relevant sections of the Final Clinical Trial Report.

Withdrawal of subjects from the study will be analysed according to the criteria in accordance with the CT Protocol. The quantitative and qualitative (in accordance with the procedures set out in the protocol) determination will be carried out for all biosamples received for analysis and not rejected for quality attributes, including the biosamples of subjects who were discontinued from the study.

A repeated analysis with the use of archival biosamples (provided such a sample is stable and meets the required quality attributes at the time of repeated analysis) must be conducted as needed in all cases of confirmed inability to obtain a reliable result:

- when confirming the fact of mixing of biosamples;
- when confirming the error of an operator/person responsible during sample preparation, carrying out the analytical procedure and during the post-analytical period;
- when lacking sufficient amount of biomaterial;
- in the event of technical problems with equipment or reagents, the conditions of transport and/or storage of biosamples.

The statistical analysis will not include the results of those subjects for whom the data obtained will be unsuitable for analysis. Such data shall be excluded from the calculations.

6.3.17 Unscheduled visit.

An unscheduled visit may be conducted at any time throughout the clinical study at the patient's request or at the discretion of the Responsible Investigator and/or co-investigator.

The date of and reason for the unscheduled visit, and the data obtained during the visit will be recorded in the source medical documentation and the eCRF.

The following can be the reasons for an unscheduled visit:

- An emergent AE/AR or observation of the course of an AE/AR;
- Assessment of changes in patient's condition over time;
- Assessment of changes in instrumental findings over time;
- Assessment of changes in laboratory findings over time;
- Substantial changes in concomitant therapy, which may affect the patient's safety;
- Another important reason (must be specified).

During an unscheduled visit, depending on the reason for conducting the visit, the following clinical study procedures may be performed:

- Anthropometric data (body weight);

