9. STATISTICS

9.1. Contents of statistical analysis

Subjects who withdrew during the screening phase are not counted in the efficacy and safety analysis since they have not received any administration of the investigational medicinal product (IMP).

Subjects who have not received a full IMP course are included in the safety analysis, but are not included in the efficacy analysis.

Subjects who discontinued from the study after completing IMP administration during the follow-up period are included in the efficacy and safety analysis. The data of such subjects are evaluated by parameters that may be analysed at a certain time point. The dropped data are not analysed.

Subjects who received at least one dose of the IMP but withdrew from the study prematurely are included by the Investigator in the tolerability analysis of the investigational product.

Statistical analysis:

Populations for statistical analysis:

ITT (Intention-to-treat population) includes all study subjects who received the investigational product at least once. The data obtained from this sample will be used for the safety analysis.

PP (Per Protocol) includes all patients who complied with the protocol requirements. This population includes all patients who received full protocol therapy, who underwent all scheduled visits, and did not have significant protocol deviations. The data obtained from this sample will be used for analysis by efficacy criteria.

The main efficacy analysis is performed on the PP population, and the additional, confirmatory analysis is performed on the ITT population (all subjects who received ≥ 1 dose and who meet the inclusion criteria, and for whom efficacy can be established).

Plan of statistical analysis of CS results

Statistical analysis is performed by a qualified biostatistician, a third party contracted by the Sponsor. Statistical analysis includes the following:

- description of patients enrolled in the study;
- the number of drop-out subjects;
- the number of adverse events;
- efficacy analysis in the group;
- tolerability assessment in the group;
- safety assessment in the group;
- analysis of pharmacokinetic data;
- statistical inferences.

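### The LOCF rule in Section 9.9 does not exempt IgG data: it overstates missed post-peak BIOVEN samples and can mask a fall in on-treatment troughs

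*Protocol*

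**What the plan says.** Section 9.9 is two sentences long. The first reads "Missing or incomplete data shall be replaced using the Last-Observation-Carried-Forward (LOCF) method". The second adds a fallback: "Or by rank aggregation technique for rows where the last observation carried forward is not applicable". It does not say when LOCF is inapplicable or how the fallback works, and no variable or analysis is exempted.

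Other parts of the protocol bear on the same data:

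- Section 6.3.9: when a PK sample is missed, the reason is recorded and "sample collection shall be resumed at the next time scheduled according to the Schedule". Section 6.3.13 says much the same. Gaps inside a profile are therefore expected, and neither section says how to analyse them.
- Section 4.2: the BIOVEN profile has "a total of 8–9 sampling time points" (Table 4.2.3: pre-dose, 15 min, 1 h, days 1, 3, 7, 14, 21 and, where applicable, 28).
- Section 9.7: "AUC0-t was calculated using trapezoidal method", and Cmax is taken "as the largest of the measured concentrations in each patient".
- Section 6.3.16, on results unsuitable for analysis: "Such data shall be excluded from the calculations".
- Section 9.1, at the end of the paragraph on subjects who leave during follow-up after completing the product: "The dropped data are not analysed".

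The BIOVEN profile is used to confirm or recalculate the dose adjustment factor (4.2, 6.3.9), and BIOVEN AUC is the comparator for steady-state AUC on the study product (9.6). Monthly troughs after month 4 are the primary PK variable (4.1).

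**The concern.** LOCF assumes that the quantity would have stayed where it was last seen. An IgG profile after an intravenous infusion falls from the peak to the next dose, so the assumption is wrong in a known direction at every post-peak point. The trapezoid in Section 9.7 needs no filled-in value for an interior gap, so LOCF adds error where none is necessary.

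Two results are exposed. The first is the BIOVEN AUC, half-life and elimination constant behind the AUC comparison and the factor check. The second is the on-treatment trough series: if a patient's trough is falling and a visit is missed, LOCF records the earlier, higher value. Overstating BIOVEN AUC works against the study product; masking a trough decline works in its favour. The two errors affect different objectives and cannot be assumed to cancel.

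**Working it through.** The protocol gives no figure for the effect of this rule, so there is none to reproduce. The sizes below need a curve shape that the protocol does not give, so it is assumed and varied.

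**Inputs.** Sampling times: Table 4.2.3, 28-day interval. AUC method: linear trapezoid (9.7). Assumed: steady state, terminal half-life h = 20, 30 or 40 days, either mono-exponential or with 35% of each dose's rise decaying with a half-life of 1.5 days.

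**One case in full: mono-exponential, h = 30.** In units of the rise per dose, C(t) = 2^(−t/30) / (1 − 2^(−28/30)). This gives C(7) = 1.786, C(14) = 1.519, C(21) = 1.292 and C(28) = 1.099. The trapezoid over all nine points is 43.35.

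- Day 14 missed, LOCF: the value becomes 1.786, and 1.786/1.519 − 1 = +17.6%. The trapezoid weight of day 14 is (21 − 7)/2 = 7 days, so AUC rises by 7 × (1.786 − 1.519) = 1.87, and 1.87/43.35 = +4.3%.
- Day 14 missed, point skipped: days 7–21 contribute 7 × (1.786 + 1.292) = 21.55 instead of 21.41, a change of 0.14, or +0.3%.
- Day 28 missed, LOCF: the value is overstated by 1.292/1.099 − 1 = +17.6%; AUC rises by 3.5 × (1.292 − 1.099) = 0.68, or +1.6%.
- Day 28 missed, simply omitted: AUC loses 3.5 × (1.292 + 1.099) = 8.37, or −19.3%.

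**Range over the six assumed curves.**

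| Missed sample | Concentration under LOCF | AUC0-28 under LOCF | AUC0-28, point left out |
|---|---|---|---|
| Day 14 | +13% to +30% | +3.2% to +6.8% | +0.2% to +0.9% |
| Day 28 | +13% to +28% | +1.2% to +2.0% | −16% to −21% (cut short) |

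A second set of assumed curves (peak 17 g/L, trough 7 g/L, half-lives 25–35 days, interval 21 or 28 days) gave +0.4% to +6.5% for any one interior point from day 1 on, against +0.1% to +2.3% when it was skipped.

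**Terminal half-life and AUC to infinity.** If the slope is fitted to the last three samples (an assumption; 9.7 says only that the method is model-independent), the fitted slope on days 14, 21 and 28 is [ln C(28) − ln C(14)]/14. Setting C(28) = C(21) halves it on a mono-exponential tail, so the half-life doubles, for example from 30 to 60 days. AUC0-∞ then rises by 58–78% across the six curves.

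**Weight in the cohort.** Section 9.2 plans 8–10 adults per cohort. One profile shifted by 3–7% moves the mean by about 3/10 = 0.3% to 7/8 = 0.9%.

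**Troughs (illustration).** Start at an assumed 8 g/L and fall 10% a month: 7.20, 6.48, 5.83, 5.25, 4.72, 4.25; mean 5.62. With the last two missing, LOCF records 5.25 twice. The final value then sits above the protocol's 5 g/L criterion instead of below it, and the mean becomes 5.88 (+4.5%). At 5% a month the final 5.88 is recorded as 6.52 and the mean is 2.4% too high. A bare average of the four observed values would be 6.19, further off still, so removing LOCF has to go with a model that contains time.

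**The case against.** The best defence is that the PK text governs PK data: Cmax comes from measured concentrations, unsuitable results are excluded, and a missed sample is only to be explained. On that reading 9.9 never reaches the profiles. But none of those sentences exempts a missed PK sample, and 9.9 is unqualified. The gap is at least an exemption that has to be written down. It is also fair that no missingness rate is known and that the effect of one profile on a cohort mean is small.

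Several stronger readings are tempting and not supported:

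- That every missing value is filled by LOCF. The fallback exists, though it is undefined.
- That Section 9.1 flatly contradicts 9.9. Its sentence on dropped data concerns only subjects who leave in follow-up after completing the product, by when both PK profiles have been taken. The conflict is real but narrow.
- That the reference troughs are distorted. For previously treated patients, two measured pre-dose values after consent are an entry condition (5.1), so the minimum reference set is observed.
- That infection counts are projected over unobserved time. Nothing says so, and the per-protocol set, on which the main efficacy analysis rests, requires all scheduled visits.
- That LOCF biases the two products' AUCs in opposite directions. On an illustrative weekly profile of the study product the effect ran from −0.6% to +1.4%, small and of mixed sign.
- That any trough fall is hidden. Only falls at missed visits are; observed ones remain.

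**Conclusion.** The point holds for IgG data. Applied as written, Section 9.9 overstates a missed post-peak BIOVEN sample, that patient's AUC and the terminal half-life, and it can mask a decline in on-treatment troughs at missed visits.

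The direction for BIOVEN follows from a falling curve and, measurement error aside, needs no assumed parameters. It does not cover the 15-minute sample, which would take the low pre-dose value, with an AUC effect of only about −0.1%. The sizes rest on the assumed half-life of 20–40 days and describe one patient; the total effect depends on how many samples are missed. The trough figures are illustrations, and a rising trough would be understated instead.

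This should be corrected before analysis. It does not show that the trial's conclusions would be wrong.

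**What to change.** In Section 9.9, remove LOCF and the undefined fallback for IgG concentrations and troughs, and state instead:

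1. AUC0-t is calculated by trapezoid on observed samples at actual sampling times, with no imputation of interior points.
2. If the last sample of the interval is missing, the curve is extrapolated to the end of the interval from the observed terminal slope, or the profile is left out of the AUC comparison. Choose one in advance; simple omission would cut AUC by about 16–21% on a 28-day interval.
3. On-treatment troughs are analysed on observed values, for example with a repeated-measures model including visit, plus a sensitivity analysis.
4. In the ITT analysis, infections are counted over observed patient-time.

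Then reconcile 9.9 with 6.3.16, 9.1 and 9.7, so that one rule covers missing, unsuitable and dropped data. If an SAP exists, it should carry the same text; an SAP that departs from 9.9 without an amendment would contradict the protocol.

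The cost is an amendment of wording and slightly more analysis work. No extra visits, samples or patients are needed.
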